14.2 DNMTi (DECITABINE AND CEDAZURIDINE)

DNMTi is a combination of decitabine, a nucleoside metabolic inhibitor, and cedazuridine, a cytidine deaminase inhibitor, indicated for treatment of adult patients with myelodysplastic syndromes (MDS).

14.2.1 Source/Acquisition and Accountability

For subject administration, decitabine and cedazuridine will be purchased by the NIH Clinical Center Pharmacy Department from commercial sources.

14.2.2 Toxicity

Fatal and serious myelosuppression and infectious complications can occur. Can cause fetal harm. Most common adverse reactions (incidence $\geq 20\%$) are fatigue, constipation, hemorrhage, myalgia, mucositis, arthralgia, nausea, dyspnea, diarrhea, rash, dizziness, febrile neutropenia, edema, headache, cough, decreased appetite, upper respiratory tract infection, pneumonia, and transaminase increased. The most common Grade 3 or 4 laboratory abnormalities ($\geq 50\%$) were leukocytes decreased, platelet count decreased, neutrophil count decreased, and hemoglobin decreased. [\[105, 118, 119\]](#)

14.2.3 Formulation and preparation

DNMTi (decitabine and cedazuridine) tablets, for oral use contain 35 mg decitabine and 100 mg cedazuridine. The tablets are biconvex, oval-shaped, film-coated, red and debossed with "H35" on one side. Each film-coated tablet contains the following inactive ingredients: lactose monohydrate, hypromellose, croscarmellose sodium, colloidal silicon dioxide, and magnesium stearate. The film coating material contains polyvinyl alcohol, titanium dioxide, polyethylene glycol, talc, and iron oxide red.

14.2.4 Stability and Storage

The tablet should be stored at 20°C to 25°C. Excursions of the tablet are permitted to 15°C to 30°C. Any unused portion of the tablet should be discarded using special handling and disposal procedures.

14.2.5 Administration procedures

The tablet should be taken on an empty stomach, 2 hours before or 2 hours after meals, and at the same time each day.

Tablet should be swallowed whole, and may not be crushed, cut, or chewed.

If a dose is missed within 12 hours of the time it is usually administered, administer the missed dose as soon as possible and then resume the normal daily dosing schedule. Extend the dosing period by 1 day for every missed dose to complete 5 daily doses for each cycle. If a dose is vomited, do not administer an additional dose (continue with the next scheduled dose).

14.2.6 Incompatibilities

Avoid coadministration of DNMTi with drugs that are metabolized by cytidine deaminase (CDA) enzymes.

16 LIST OF ABBREVIATIONS

Abbreviation	Term
ACAT	Ability to Consent Assessment Team
AE	Adverse Event/Adverse Experience
AESI	Adverse Event/Experience of Special Interest
ANC	Absolute neutrophil count
BTRIS	Biomedical Translational Research Information System
CCR	Center for Cancer Research
CDA	Confidential Disclosure Agreement
CFR	Code of Federal Regulations
CNS	Central nervous system
CONSORT	Consolidated Standards of Reporting Trials
COV	Close-out Visit
CR	Complete Response
CSR	Clinical Study Report
CRADA	Cooperative Research and Development Agreement
CT	Computed Tomography
CTA	Clinical Trials Agreement
CTCAE	Common Terminology Criteria for Adverse Events
DLT	Dose-limiting toxicity
DSMB	Data Safety Monitoring Board (DSMB)
DTA	Data Transfer Agreement
EC	Ethics Committee
eCRF	Electronic Case Report Form
ECOG	Eastern Cooperative Oncology Group
EFS	Event-free survival
EKG	Electrocardiogram
FDA	Food and Drug Administration
FWA	Federal-Wide Assurance
GCP	Good Clinical Practice
GDS	Genomic Data Sharing
GLP	Good Laboratory Practices
GMP	Good Manufacturing Practices
HBV	Hepatitis B virus
HCV	Hepatitis C virus
HHS	Health and Human Services
HIV	Human immunodeficiency virus
IB	Investigator's Brochure
IBC	Institutional Biosafety Committee
ICD/ICF	Informed Consent Document/Form
ICH	International Council for Harmonisation
IMV	Interim Monitoring Visit

Abbreviation	Term
IND	Investigational New Drug
IRB	Institutional Review Board
IRBO	Institutional Review Board Office
IV	Intravenous
LAR	Legally Authorized Representative
MRI	Magnetic Resonance Imaging
MTA	Material Transfer Agreement
MTD	Maximal tolerated dose
N	Number (typically refers to subjects)
NCT	National Clinical Trial (number)
NDA	New Drug Application
NIH	National Institutes of Health
NOS	Not otherwise specified
OHSRP	Office for Human Subjects Research Protections
OHRP	Office for Human Research Protections
OS	Overall survival
OSRO	Office of Sponsor and Regulatory Oversight
PD	Progressive Disease
PET	Positron Emission Tomography
PFS	Progression-free survival
PI	Principal Investigator
PR	Partial Response
PS	Performance Status
QA	Quality Assurance
QC	Quality Control
rCR	Revised Common Rule
RECIST	Response Evaluation Criteria in Solid Tumors
RP2D	Recommended Phase II dose
SAE	Serious Adverse Event/Serious Adverse Experience
SAV	Site Assessment Visit
SIV	Site Initiation Visit
SD	Stable Disease
SMC	Safety Monitoring Committee
SOP	Standard Operating Procedure
ULN	Upper limit of normal
US	United States
WHO	World Health Organization

17 APPENDICES

17.1 APPENDIX A: PERFORMANCE STATUS CRITERIA

ECOG Performance Status Scale		Karnofsky Performance Scale	
Grade	Descriptions	Percent	Description
0	Normal activity. Fully active, able to carry on all pre-disease performance without restriction.	100	Normal, no complaints, no evidence of disease.
		90	Able to carry on normal activity; minor signs or symptoms of disease.
1	Symptoms, but ambulatory. Restricted in physically strenuous activity, but ambulatory and able to carry out work of a light or sedentary nature (e.g., light housework, office work).	80	Normal activity with effort; some signs or symptoms of disease.
		70	Cares for self, unable to carry on normal activity or to do active work.
2	In bed <50% of the time. Ambulatory and capable of all self-care, but unable to carry out any work activities. Up and about more than 50% of waking hours.	60	Requires occasional assistance, but is able to care for most of his/her needs.
		50	Requires considerable assistance and frequent medical care.
3	In bed >50% of the time. Capable of only limited self-care, confined to bed or chair more than 50% of waking hours.	40	Disabled, requires special care and assistance.
		30	Severely disabled, hospitalization indicated. Death not imminent.
4	100% bedridden. Completely disabled. Cannot carry on any self-care. Totally confined to bed or chair.	20	Very sick, hospitalization indicated. Death not imminent.
		10	Moribund, fatal processes progressing rapidly.
5	Dead.	0	Dead.

17.2 APPENDIX B: 2016 WHO CLASSIFICATION FOR MYELODYSPLASTIC SYNDROME

Myelodysplastic syndromes (MDS)

- **MDS with single lineage dysplasia (MDS-SLD)**
- **MDS with ring sideroblasts (MDS-RS)**
 - **MDS-RS and single lineage dysplasia**
 - **MDS-RS and multilineage dysplasia**
- **MDS with multilineage dysplasia (MDS-MLD)**
- **MDS with excess blasts**
- **MDS with isolated del(5q)**
- **MDS, unclassifiable**
- ***Provisional entity: Refractory cytopenia of childhood***

17.3 APPENDIX C: REVISED INTERNATIONAL PROGNOSTIC SCORING SYSTEM (IPSS-R) FOR MYELODYSPLASTIC SYNDROMES

Prognostic variable	Score						
	0	0.5	1.0	1.5	2.0	3.0	4.0
Cytogenetics*	Very good		Good		Intermediate	Poor	Very poor
Bone marrow blast (percent)	≤2		>2 to <5		5 to 10	>10	
Hemoglobin (g/dL)	≥10		8 to <10	<8			
Platelets (cells/microL)	≥100	50 to 100	<50				
Absolute neutrophil count (cells/microL)	≥0.8	<0.8					
Risk group		IPSS-R score		Median overall survival (years)		Median time to 25 percent AML evolution (years)	
Very low		≤1.5		8.8		>14.5	
Low		>1.5 to 3.0		5.3		10.8	
Intermediate		>3 to 4.5		3.0		3.2	
High		>4.5 to 6		1.6		1.4	
Very high		>6		0.8		0.7	

AML: acute myeloid leukemia; MDS: myelodysplastic syndromes.

* Cytogenetic definitions:

Very good: -Y, del(11q)

Good: Normal, del(5q), del(12p), del(20q), double including del(5q)

Intermediate: del(7q), +8, +19, i(17q), any other single, double not including del(5q) or -7/del(7q), or independent clones

Poor: -7, inv(3)/t(3q)/del(3q), double including -7/del(7q), complex: 3 abnormalities.

Very poor: Complex: >3 abnormalities

This research was originally published in Blood. Greenberg PL, Tuechler H, Schanz J, et al. Revised International Prognostic Scoring System (IPSS-R) for myelodysplastic syndromes. Blood 2012. Copyright © 2012 the American Society of Hematology.

17.4 APPENDIX D: THE 2006 INTERNATIONAL WORKING GROUP RESPONSE CRITERIA WITH MODIFIED DEFINITIONS FOR HEMATOLOGIC IMPROVEMENT BY THE 2018 INTERNATIONAL WORKING GROUP RESPONSE CRITERIA.[85]

Category	Response criteria (responses must last at least 4 weeks)
Complete remission	
• Bone marrow: $\leq 5\%$ myeloblasts with normal maturation of all cell lines*• Persistent dysplasia will be noted*• Peripheral blood†
• Hgb ≥ 11 g/dL• Platelets $\geq 100 \times 10^9/L$• Neutrophils $\geq 1.0 \times 10^9/L$• Blasts 0%
Partial remission	All CR criteria if abnormal before treatment except: 
• Bone marrow blasts decreased by $\geq 50\%$ over pretreatment but still $>5\%$• Cellularity and morphology not relevant
Marrow CR	
• Bone marrow: $\leq 5\%$ myeloblasts and decrease by $\geq 50\%$ over pretreatment• Peripheral blood: if HI responses, they will be noted in addition to marrow CR
Stable disease	Failure to achieve at least PR, but no evidence of progression for >8 weeks
Failure	Death during treatment or disease progression characterized by worsening of cytopenias, increase in percentage of bone marrow blasts, or progression to more advanced MDS FAB subtype than pre-treatment
Relapse after CR or PR	At least 1 of the following: 
• Return to pre-treatment bone marrow blast percentage• Decrement of $\geq 50\%$ from maximum remission/response levels in granulocytes or platelets• Reduction in Hgb concentration by ≥ 1.5 g/dL or transfusion dependence
Cytogenetic response	Complete 
• Disappearance of the chromosomal abnormality without appearance of new ones Partial 
• At least 50% reduction of the chromosomal abnormality
Disease progression	For patients with: 
• Less than 5% blasts: $\geq 50\%$ increase in blasts to $>5\%$ blasts• 5%-10% blasts: $\geq 50\%$ increase to 10% blasts

	
 • 10%-20% blasts: $\geq 50\%$ increase to $>20\%$ blasts • 20%-30% blasts: $\geq 50\%$ increase to $>30\%$ blasts 
Any of the following:
 
 • At least 50% decrement from maximum remission/response in granulocytes or platelets • Reduction in Hgb by ≥ 2 g/dL • Transfusion dependence
Survival	
Endpoints:
 
 • Overall: death from any cause • Event free: failure or death from any cause • PFS: disease progression or death from MDS • DFS: time to relapse • Cause-specific death: death related to MDS

MDS, myelodysplastic syndromes; Hgb, hemoglobin; CR, complete remission; HI, hematologic improvement; PR, partial remission; FAB, French-American-British; AML, acute myeloid leukemia; PFS, progression-free survival; DFS, disease-free survival.

To convert hemoglobin from grams per deciliter to grams per liter, multiply grams per deciliter by 10.

*Dysplastic changes should consider the normal range of dysplastic changes.

†In some circumstances, protocol therapy may require the initiation of further treatment (eg, consolidation, maintenance) before the 4-week period. Such patients can be included in the response category into which they fit at the time the therapy is started. Transient cytopenias during repeated chemotherapy courses should not be considered as interrupting durability of response, as long as they recover to the improved counts of the previous course.

Hematologic Improvement

Category	Patient pre-trial baseline	Response criteria	
Erythroid response (HI-E)	No Transfusion Dependence at baseline (0 RBC transfusions in 16 weeks)	At least 2 consecutive Hgb measurements ≥ 1.5 g/dL for a period of minimum 8 weeks in an observation period of 16 to 24 weeks compared with the lowest mean of 2 Hgb measurements (apart from any transfusion) within 16 weeks before treatment onset; only a response duration of at least 16 weeks, however, is considered clinically meaningful	
	Low Transfusion Dependence at baseline (3-7 RBC transfusions in 16 weeks in at least 2 transfusion episodes, maximum 3 in 8 weeks)	Transfusion independence, defined by the absence of any transfusions for at least 8 weeks in an observation period of 16-24 weeks with the same transfusion policy compared with 16 weeks prior to treatment; only a response duration of at least 16 weeks, however, is considered clinically meaningful	
	High Transfusion Dependence at baseline (≥ 8 RBC transfusions in 16 weeks)	Major response	Transfusion independence, defined by the absence of any transfusions over a period of minimum 8 weeks in an

	weeks, ≥ 4 transfusion episodes in 8 weeks)		observation period of 16-24 weeks with the same transfusion policy compared with 16 weeks prior to treatment; only a response duration of at least 16 weeks, however, is considered clinically meaningful
		Minor response	Transfusion independence, defined by the absence of any transfusions over a period of minimum 8 weeks in an observation period of 16-24 weeks with the same transfusion policy compared with 16 weeks prior to treatment; only a response duration of at least 16 weeks, however, is considered clinically meaningful
Platelet response (HI-P)	Pre-treatment PLT $<100 \times 10^9/L$	
 Absolute increase of $30 \times 10^9/L$ for patients starting with $>20 \times 10^9/L$ PLTs or Increase from $<20 \times 10^9/L$ to $>20 \times 10^9/L$ and by at least 100% 
In addition:
 
 In addition, evolution of bleeding symptoms is to be taken into account Increments of platelets also for patients with a pre-treatment PLT count of $\geq 100 \times 10^9$ are to be reported 	
Neutrophil response (HI-N)	Pre-treatment ANC $<1.0 \times 10^9/L$	
 At least 100% increase and an absolute increase $>0.5 \times 10^9/L$ Increments of neutrophils also for patients with a pre-treatment ANC of $\geq 1.0 \times 10^9/L$ are to be reported 	

17.5 APPENDIX E: BLOOD AND MARROW PROCESSING CORE PROTOCOLS

Anti-IL8 in MDS (IRB 000356):

1. Peripheral Blood: 2 x 5 mL SST tubes (1 tube for Antibody PK, 1 tube for free IL8 assay, protocols below)
2. Peripheral Blood: 1 x 10mL EDTA tube (for separation and storage of MNC and plasma, protocol below)
3. Peripheral Blood: 1 x 2.5mL Paxgene Tube (for storage, see protocol below)
4. Bone Marrow: 1 x 10mL EDTA tube (for separation and storage of MNC and plasma, protocol below)
5. Bone Marrow: 1 x 2.5mL Paxgene Tube (for storage, see protocol below)

Processing Protocols:

Bone Marrow and Peripheral Blood Processing from EDTA tubes

1. Spin the bone marrow (BM) aspirate or peripheral blood (PB) at 2500 rpm (1500 rcf) for 5 minutes to isolate neat plasma prior to adding the PBS/Ficoll.
2. Store 5 x 300uL aliquots of plasma at -80deg C.
3. Add 2 volumes of PBS to the PB/BM and be sure to mix well to ensure a good underlay of the Ficoll.
4. Add a 1:1 volume of Ficoll to the diluted BM/PB by carefully dispensing at the bottom of the conical tube. The BM/PB should lay on top of the Ficoll layer. Try not to mix the Ficoll and BM/PB.
5. Spin the tubes at 3000 rpm (2000 rcf) for 15 minutes.
6. The mononuclear layer interface will lay between the Ficoll and plasma/PBS layers and will often appear whitish if there is a larger number of cells. Carefully remove this interface taking as little Ficoll as possible. If you cannot see the layer, just remove several mL from on top of the Ficoll layer, this will contain all the cell. Dilute the interface containing the cells, with 4 volumes of RPMI (supplemented with 10%FBS, and 1% Pen/Strep). The remaining Ficoll and RBCs at the bottom of the tube can be discarded.
7. Spin the mononuclear cells at 1000rpm for 5 min.
8. Resuspend the cell pellet in 10 to 40ml of RBC Lysis Buffer (ie; Qiagen RBC Lysis Buffer). The volume of lysis buffer depends on the cell pellet. For very small pellets use 10mL, for very large pellets, use 40mL RBC lysis .
9. Resuspend the cells in RPMI (supplemented with 10%FBS, and 1% Pen/Strep) and count the cells using a hemacytometer.
10. Freeze the cells in 10% DMSO, 20% FBS, and 70% RPMI with no more than 10million cells per mL and 1 mL per cryotube. Freeze samples either using a cell freezer container in a -80deg C freezer (i.e.; [name] container) or a controlled rate freezer. Once cells have reached -80deg C, transfer cryotubes to a liquid nitrogen cryounit.

Antibody PK Studies (IL8 study), Peripheral Blood Processing from SST Tube:

1. Blood samples will be collected by direct venipuncture or through an indwelling catheter. If a catheter is used for blood collection, then approximately 1mL of blood should be

withdrawn initially then discarded. Only saline is permitted to keep catheters patent, unless discussed and agreed upon by the Sponsor. If samples are obtained through a heparin lock, sufficient blood (~1mL) must be withdrawn to remove the heparin solution.

2. Immediately after collection, gently invert each tube 5 times and allow blood to clot for 30-45m at room temperature (tube standing upright).
3. Centrifuge samples at 4deg C for 10min (singing buckets) or 15 minutes (fixed buckets) at 100-1300g until clot and serum are well separated. Note: If refrigerated centrifuge is not available, prechill centrifuge tube holders at -20deg C for 20m prior to centrifugation.
4. Transfer 1mL aliquots of serum into 4 appropriately labeled screw cap polypropylene tubes.
5. Keep samples at -80deg C until requested for shipment.

Free IL8 Studies (IL8 study). Peripheral Blood Processing from SST Tube:

1. Blood samples will be collected by direct venipuncture or through an indwelling catheter. If a catheter is used for blood collection, then approximately 1mL of blood should be withdrawn initially then discarded. Only saline is permitted to keep catheters patent, unless discussed and agreed upon by the Sponsor. If samples are obtained through a heparin lock, sufficient blood (~1mL) must be withdrawn to remove the heparin solution.
2. Immediately after collection, gently invert each tube 5 times and allow blood to clot for 30-45m at room temperature (tube standing upright).
3. Centrifuge samples at 4deg C for 10min (singing buckets) or 15 minutes (fixed buckets) at 100-1300g until clot and serum are well separated. Note: If refrigerated centrifuge is not available, prechill centrifuge tube holders at -20deg C for 20m prior to centrifugation.
4. Transfer 1mL aliquots of serum into 4 appropriately labeled screw cap polypropylene tubes.
5. Keep samples at -80deg C until requested for shipment.

PAXgene Tube Storage for BM/PB:

1. Tubes should remain upright. Incubate tubes at room temp for 2-72hrs after collection, then place at -20deg C for 24hr, then place in a -80deg C freezer.

17.6 APPENDIX F: CLINICAL DATA ELEMENTS FOR CRF ENTRY IN CLINICAL DATABASE

Patient (recipient) characteristics at protocol entry

- Sex (male, female)
- Age at enrollment (number)
- Ethnicity (white, black, American Indian/Alaskan native, Asian/Pacific islander, Hispanic, other)
- ECOG and Karnofsky performance status
- Diagnosis - MDS (high risk or low risk)
- 2016 WHO classification of MDS (MDS with single lineage dysplasia [MDS-SLD], MDS with ring sideroblasts and single lineage dysplasia [MDS-RS-SLD], MDS with ring sideroblasts and multilineage dysplasia [MDS-RS-MLD], MDS with multilineage dysplasia [MDS-MLD], MDS with excess blasts [MDS-EB], MDS with isolated del(5q), MDS unclassifiable [MDS-U],
- Date of MDS diagnosis (month, year)
- Age at MDS diagnosis
- Revised International Prognostic Scoring System (IPSS-R) score at MDS diagnosis
- Cytogenetic profile at diagnosis and enrollment, if available (see Appendix C)- only need overall score (very good, good, intermediate, poor, very poor)
- Bone marrow blasts %, if available
- Hemoglobin, if available
- Platelet count, if available
- Absolute neutrophil count (ANC), if available
- RBC transfusion dependance (transfusion dependent or independent)
- Platelet transfusion dependance (transfusion dependent or independent)
- Average # of transfusions per month (RBCs units and instances of platelets transfusions) in the 3 months leading up to baseline on study
- Laboratory values will be collected from time of screening for duration of trial
- TP53 mutation status at enrollment, if available (TP53 mutation positive or negative)
- Names and # of cycles of prior Lines of therapy for MDS.
- Response to most recent line of therapy: CR (complete response), PR (partial response), HI (hematologic improvement), mCR with HI (marrow CR with hematologic improvement), mCR without HI (marrow CR without hematologic improvement), SD (stable disease), PD (disease progression)
- MDS-CI (low risk, intermediate risk, high risk)
- Rockwood frailty index (see Clinical Frailty Scale)
- Disease status at time of enrollment: CR (complete response), PR (partial response), HI (hematologic improvement), mCR with HI (marrow CR with hematologic improvement), mCR without HI (marrow CR without hematologic improvement), SD (stable disease), PD (disease progression)
- Patient Reported Outcome Questionnaires (per section [3.5.3](#))
 - Subjects > 18 years of age:
 1. EORTC QLQC30 score (patient reported)- see questionnaire
 2. NIH developed psychosocial assessment scale – see questionnaire

Data collection during study/treatment

- Cycle number & day of treatment
- Study Drug Administration
- Disease response at assessment timepoints: CR (complete response), PR (partial response), HI (hematologic improvement), mCR with HI (marrow CR with hematologic improvement), mCR without HI (marrow CR without hematologic improvement), SD (stable disease), PD (disease progression)
- Best overall response to study treatment: CR (complete response), PR (partial response), HI (hematologic improvement), mCR with HI (marrow CR with hematologic improvement), mCR without HI (marrow CR without hematologic improvement), SD (stable disease), PD (disease progression)
- Bone marrow percent blasts
- RBC transfusion dependence (transfusion dependent or transfusion independent)
- Platelet transfusion dependence (transfusion dependent or transfusion independent)
- # of transfusions per month (RBCs units and instances of platelets transfusions)
- Adverse events
- Patient Reported Outcome Questionnaires: (per section [3.5.3](#))
 - EORTC QLQC30 score (patient reported) – see questionnaire
 - NIH developed psychosocial assessment scale – see questionnaire

Data collection at post-therapy follow-up visits

- Alive (yes/no)
- Adverse events
- Progression of MDS (if yes, to what and when)
- Diagnosed with sAML (yes/no)
 - If diagnosed with sAML, date of sAML diagnosis (month, year)
 - subsequent MDS/AML specific treatments including BMT until off study if information available.

Data collection at time of death

- Date of death
- Disease status at time of death: CR or not CR
- Cause of death: disease progression/relapse vs non-relapse mortality (definition of non-relapse mortality: subject in clinical remission at time of death)
- If non-relapse mortality, primary cause of death (e.g., infection, organ failure, other – per CTCAE)

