1.2 BACKGROUND AND RATIONALE

1.2.1 Myelodysplastic syndromes

The myelodysplastic syndromes (MDS) are a group of heterogenous clonal neoplasms of hematopoietic stem cells, characterized by dysplastic changes in at least one myeloid lineage, recurrent genetic aberrations, presence of up to 20% myeloblasts in the bone marrow, and high risk of evolution to acute myelogenous leukemia (AML).^[1] Myelodysplasia results in ineffective hematopoiesis with consequential peripheral blood cytopenia(s). Anemia is the most

common clinical presentation of MDS, but other cytopenias are also often present. Cytopenia, together with ineffective maturation of neutrophils and platelets, often result in severe and/or recurrent infections and/or bleeding episodes, respectively. In general, it is estimated that up to 1/3 of participants with MDS will die from cytopenia-related complications, up to 1/3 have disease progression into a secondary AML with poor prognosis, and the remaining 1/3 may die from causes unrelated to their MDS.[2, 3]

MDS is a disease of the elderly, with a median age at diagnosis of approximately 75 years, with ~80% of participants being ≥ 65 years.[4] Based on cancer registry data, about 10,000 new MDS cases are diagnosed per year in the United States,[5, 6] but the number is probably underestimated[7] and may be as high as $>40,000$ based on Medicare claims analyses.[8] There is a slight predominance of males.[4]

Most MDS participants (~90%) have sporadic disease and the remainder are therapy-related MDS (t-MDS), the latter often presenting in participants younger than 60 years of age. In the last decade, familial related myeloid neoplasia in persons with germ-line mutations (i.e. *RUNX1*, *GATA2*, *DDX41*, *CEPBA*, *ANKRD26*, *ETV6*) is recognized as a predisposing condition for earlier acquisition of additional MDS-related mutations and MDS development.[9] Additionally, MDS can also develop from the rare inherited bone marrow failure disorders, such as Fanconi and Diamond-Blackfan anemia, which can present in childhood and adolescence.[10]

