Survival	Endpoints: 
 Overall: death from any cause Event free: failure or death from any cause PFS: disease progression or death from MDS DFS: time to relapse Cause-specific death: death related to MDS

MDS, myelodysplastic syndromes; Hgb, hemoglobin; CR, complete remission; HI, hematologic improvement; PR, partial remission; FAB, French-American-British; AML, acute myeloid leukemia; PFS, progression-free survival; DFS, disease-free survival.

To convert hemoglobin from grams per deciliter to grams per liter, multiply grams per deciliter by 10.

*Dysplastic changes should consider the normal range of dysplastic changes.

†In some circumstances, protocol therapy may require the initiation of further treatment (eg, consolidation, maintenance) before the 4-week period. Such participants can be included in the response category into which they fit at the time the therapy is started. Transient cytopenias during repeated chemotherapy courses should not be considered as interrupting durability of response, as long as they recover to the improved counts of the previous course.

Hematologic Improvement

Category	Participant pre-trial baseline	Response criteria
----------	--------------------------------	-------------------

Erythroid response (HI-E)	No Transfusion Dependence at baseline (0 RBC transfusions in 16 weeks)	At least 2 consecutive Hgb measurements ≥ 1.5 g/dL for a period of minimum 8 weeks in an observation period of 16 to 24 weeks compared with the lowest mean of 2 Hgb measurements (apart from any transfusion) within 16 weeks before treatment onset; only a response duration of at least 16 weeks, however, is considered clinically meaningful
	Low Transfusion Dependence at baseline (3-7 RBC transfusions in 16 weeks in at least 2 transfusion episodes, maximum 3 in 8 weeks)	Transfusion independence, defined by the absence of any transfusions for at least 8 weeks in an observation period of 16-24 weeks with the same transfusion policy compared with 16 weeks prior to treatment; only a response duration of at least 16 weeks, however, is considered clinically meaningful

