10.4.3 Analysis of the Secondary Endpoint(s)

- The secondary objectives for phase I are to describe pharmacokinetic properties of BMS-986253 in MDS participants and to evaluate safety and tolerability of BMS-986253 in MDS participants. The AUC, half-life, and Css of BMS-986253 will be evaluated in participants, separately by dose level and cohort using descriptive statistics.
- The secondary objectives for phase II are:
 - (a) to evaluate the safety and tolerability of the agent as measured by the grades and types of toxicity noted for the agent at each dose level, separately by cohort; and,
 - (b) to evaluate efficacy, as measured by clinical outcomes, including OIR (CR + PR + HI + marrow CR + SD), cytogenetic response rate, time to best response, disease free survival (DFS; definition: time to relapse for participants who achieve CR), progression free survival (PFS; definition: disease progression or death from MDS), leukemia free survival (LFS; definition: progression to AML or death from any cause), and overall survival (OS; definition: death from any cause).
 - OIR and cytogenetic response rate will each be reported as a fraction, separately by cohort, along with a 95% confidence interval. Time to best response, DFS,

PFS, LFS, and OS will be evaluated separately for each phase II cohort using the Kaplan-Meier method. In each case, the median time to event will be reported along with a 95% confidence interval for the median.

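### The death form ties cause of death to remission status, so it cannot identify death from MDS, which the PFS definition requires

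*Combined protocol and SAP*

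**What the plan says.** Appendix F (17.6) lists three items at death besides the date.

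- Disease status, with two levels: "Disease status at time of death: CR or not CR".
- Cause, with two categories: "Cause of death: disease progression/relapse vs non-relapse mortality (definition of non-relapse mortality: subject in clinical remission at time of death".
- A specific cause such as infection or organ failure, which is conditional: "If non-relapse mortality, primary cause of death".

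Clinical remission is not defined; the neighbouring status item suggests CR.

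Section 10.4.3 defines "progression free survival (PFS; definition: disease progression or death from MDS" and plans Kaplan-Meier medians with 95% confidence intervals by phase II cohort. Sections 1.1.2.2, 3.5.2, 6.3.1 and 10.1 give the same definition. The two other endpoints that count deaths do not depend on cause: "overall survival (OS; definition: death from any cause" and "leukemia free survival (LFS; definition: progression to AML or death from any cause".

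The survival row of section 6.3.1 also lists "Cause-specific death: death related to MDS". That measure does not appear among the objectives, the section 10.1 endpoints or the section 10.4 analyses.

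**The concern.** The form uses remission status as a stand-in for cause of death. That works where nearly everyone who has not relapsed is in remission. It does not work in MDS, where participants can live for long periods with stable disease, hematologic improvement, PR or marrow CR. If such a participant dies of a stroke or an unrelated infection, the stated rule leads to progression/relapse, and the question about the actual cause is never reached.

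PFS needs exactly that attribution. No adjudication rule elsewhere in the plan says how death from MDS is to be established. Extra deaths counted as events would make PFS look shorter than the endpoint as defined. A cause not asked for at the time may also be hard to recover years later.

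**Working it through.** No sample size, error rate or event count rests on this form, so there is no planned figure to reproduce. The check has three steps.

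**1. Form against endpoint.** With clinical remission read as CR:

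| Status at death | True cause | Code under Appendix F | Specific cause on form | PFS event by definition | PFS event if the form decides |
|---|---|---|---|---|---|
| CR | Not MDS | Non-relapse | Yes | No | No |
| SD, HI, PR or marrow CR, no prior progression | Not MDS | Progression/relapse | No | No | **Yes** |
| SD, HI, PR or marrow CR, no prior progression | MDS | Progression/relapse | No | Yes | Yes |
| Progression already recorded | Any | Progression/relapse | No | Already counted | Already counted |

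Only the second row goes wrong for PFS. A broader reading of remission would move PR or marrow CR out of that row, but not SD or HI alone.

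**2. How common that row could be.** Section 10.2 designs the LR cohort around a 40% target rate for CR, PR, or marrow CR with HI. Even at that target, 1 − 0.40 = 60% would not have such a response, and CR is only part of the 40%. This supports treating death outside CR as common. It does not give the share in CR at death.

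Let u be the share of deaths unrelated to MDS, and c the share of those deaths that occur in remission. The miscoded share of all deaths is m = u × (1 − c).

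- u from section 1.2.5: 29 unrelated against 67 MDS- or treatment-related, so 29/(29 + 67) = 29/96 = 30.2%.
- u from section 1.2.1: about one third ("the remaining 1/3 may die from causes unrelated to their MDS").
- c is not in the documents; assumed 0 to 0.5.

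| u | c = 0 | c = 0.5 |
|---|---|---|
| 29/96 | 0.302 × 1 = 30.2% | 0.302 × 0.5 = 15.1% |
| 1/3 | 33.3% | 16.7% |

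As a ceiling, if every phase II participant died, 29/96 gives 32 × 0.151 = 4.8 to 32 × 0.302 = 9.7 miscoded deaths in the HR cohort, and 25 × 0.151 = 3.8 to 25 × 0.302 = 7.6 in the LR cohort. These are deaths, not PFS events. The number that changes PFS is smaller, by an amount the documents do not allow one to calculate. Treatment-related deaths outside remission are not included, because the 67 pools them with MDS deaths.

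**3. Whether another record supplies the cause.**

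- Through 100 days after the last dose: yes. Death is an SAE criterion (8.1.2), and each SAE carries relationship and alternate etiology (8.1.5, 8.2).
- After 100 days, related: yes. Serious related events are still recorded (6.1).
- After 100 days, unrelated: no. These need not be recorded as AEs (6.1). Follow-up is by telephone, with AEs assessed and outside records requested at the first contact only (3.4, 3.6). The death form is then the main planned source.

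**The case against.** The strongest reply is that the consequences are limited, and most of it stands.

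- A reader might infer that the safety record is corrupted. The documents do not support that. Relationship and alternate etiology for fatal SAEs are recorded outside this form. All SAEs through 100 days go to the pharmaceutical collaborator whether related or not (8.5). The phase II waiver for progression deaths has an exception where causality is suspected (8.4). What remains is that the death form may contradict the SAE record.
- A reader might infer that cause-specific death will be misreported. No analysis of it is planned, so the practical effect is on PFS.
- A reader might infer that PFS is invalid as a whole. Appendix F collects progression separately at follow-up, with type and timing, so only deaths without prior progression matter.
- The figures in section 1.2.5 describe eventual outcomes in MDS generally. Section 1.2.1 gives median OS of 1.5 years for HR-MDS and 5.9 for LR-MDS, so one unrelated share for both cohorts is a rough guide only.
- Appendix F lists data elements; the CRF itself is not in the documents and could offer more choices.

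The last point does not remove the concern. The listed definition is explicit, and whoever follows it will code these deaths as disease. The other records also leave late unrelated deaths without a cause.

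**Conclusion.** The mismatch is real and narrow. Under the rule as written, a non-MDS death outside remission is coded as progression/relapse with no cause on the form, which conflicts with a PFS definition that counts only death from MDS. About 15 to 30% of all deaths could be miscoded, or 17 to 33% on the one-third figure. This assumes that the general MDS share applies to this trial and that 0 to 50% of unrelated deaths occur in remission. The effect on PFS is smaller, and the gap is largest for unrelated deaths more than 100 days after the last dose.

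ORR, DLT/OBD, OS (which section 10.2 ranks first among the secondary endpoints), LFS, the sample size and the SAE causality records are untouched. The point is worth correcting, but its severity is below must-fix.

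**What to change.** In Appendix F:

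- Delete the definition of non-relapse mortality by remission status.
- For every death, whatever the remission status, record (a) a primary cause, for example MDS/AML progression, infection, bleeding, cardiac, organ failure, other or unknown, and (b) a separate attribution: MDS or its cytopenias, study treatment, unrelated, or unknown.
- Keep disease status at death as its own item.

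In section 10.4.3, state which attributions count as death from MDS for PFS, and how deaths with unknown attribution are handled.

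The two items must be separate. Section 1.2.1 describes infection and bleeding as consequences of cytopenia, so a code of infection alone does not show whether the death was due to MDS. Redefining PFS to count any death would remove the dependence on cause, but would change an endpoint stated in five places and still leave late deaths without a recorded cause.

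The cost is one or two CRF fields and a sentence or two of text, with no extra visits. Some late deaths learned of by telephone will be coded unknown.
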